2.4.4.2.4 Summary of results per time point

Double-blind period

Central laboratory values (in conventional (US) and international units), percent change from baseline, and/or when appropriate absolute change from baseline (in conventional and international units), for LDL-C, Total-C, HDL-C, fasting TG, non-HDL-C, at Week 8, Week 12 and Week 24 time points, for Lp(a), Apo-B, Apo-A1 and ratio Apo-B/Apo-A1 (absolute change from baseline) at Week 12 and Week 24 time points will be summarized in the ITT population and in the mITT population using:

• For lipids other than TG and Lp(a): LS mean and SE, obtained from the same MMRM models as used for endpoints above and including planned time points (see

Section 2.4.4.2.1) and with raw values, changes from baseline, or percent change from baseline as response variable in the model as appropriate.

• For TG and Lp(a): mean and SE obtained from multiple imputation approach followed by the robust regression models as used for endpoints above and including planned time points (see Section 2.4.4.2.2) and with raw values or percent changes from baseline as response variable in the model as appropriate.

In addition, quantitative descriptive summaries by time point (value at visit and % change from baseline) will be presented for all lipids using observed (ie, non-missing) data. In addition, binary variables for LDL-C will be also described by time point. For LDL-C, these summaries will be also provided according to BW stratum as per IVRS/IWRS, and according to up-titration/dose adjustment status at Week 12.

OL period

Quantitative descriptive summaries by time point will be presented for LDL-C, Total-C, HDL-C, fasting TG, and non- HDL-C, Lp(a), Apo-B, Apo-A1 and ratio Apo-B/Apo-A1 using observed data in the OL population. LDL-C will be also described by category over time.

Combined period

In each dosing regimen cohort, for patients receiving alirocumab in the double-blind period, central laboratory values (in conventional (US) and international units) including both the doubleblind and open-label period assessments, percent change from baseline, and/or when appropriate absolute change from baseline (in conventional and international units), LDL-C, Total-C, HDL-C, fasting TG, and non- HDL-C, Lp(a), Apo-B, Apo-A1 and ratio Apo-B/Apo-A1 (absolute change from baseline) at all planned time points (Week 8 to Week 104) will be summarized by patient counts, mean and SD by all patients.

2.4.4.3 Multiplicity issues

The Bonferroni adjustment will be applied to handle multiplicity for the comparison of each alirocumab dosing regimen group versus its contemporaneously randomized placebo group (ie, alirocumab Q2W versus placebo Q2W; alirocumab Q4W versus placebo Q4W) for the primary efficacy endpoint (two-sided 0.025 alpha level will apply for each comparison).

In order to handle multiple key secondary endpoints, the overall type-I error will be controlled by the use of a sequential inferential approach applied independently within each dosing regimen cohort (Q2W and Q4W). Statistical significance of the primary parameter at the two-sided 0.025 alpha level is required before drawing inferential conclusions for that dosing regimen cohort about first key secondary parameter (refer to order of list in Section 2.1.3.2.1. Inferential conclusions about successive key secondary parameters for a given dosing regimen cohort require statistical significance of the prior one in that dosing regimen cohort.

The Bonferroni adjustment and this fixed hierarchical approach will ensure a strong control of the overall type-I error rate at the two-sided 0.05 level.

No further adjustments will be made for other secondary endpoints for which p-values will be provided for descriptive purpose only (no claim).

In addition, no further multiplicity adjustment is needed for multiple analyses (ie, first step and second step analyses, if applicable, see Section 3). All primary and key secondary efficacy endpoints will be fully evaluable at the time of the first step analysis. Analyses of lipid parameters beyond Week 24 will be descriptive.

2.4.4.4 Exploratory efficacy analyses

Difference in percent change in LDL-C between the 2 alirocumab Q2W and Q4W dosing regimen cohorts

The difference in terms of percent change in LDL-C between the 2 alirocumab dosing regimen groups will be explored in the ITT population and in the mITT population.

FMD sub-study

The absolute change from baseline in FMD at Week 24 in the FMD sub-study population will be analyzed using an ANCOVA model, with unequal variances by treatment group (except if convergence issue). The model will include the fixed categorical effects of treatment group (alirocumab, placebo), the dosing regimen cohort (Q2W, Q4W) the treatment-by-dosing regimen cohort interaction and the continuous fixed covariate of baseline FMD value. Model assumptions for normality will be explored prior to the analysis testing. Throughout the ANCOVA model, least-square (LS) mean and standard error (SE) will be provided, regardless of the dosing regimen cohort, for the alirocumab group and the placebo group. LS means difference will be provided for the comparison of the alirocumab group versus the placebo group regardless of the dosing regimen cohorts with the 95% CI, using appropriate contrasts.

All Week 24 FMD values will be included in the analysis regardless of individual patient adherence to treatment.

In addition, the same statistical approach as described above will be applied but only including ontreatment values in the model (on-treatment analysis).

2.4.5 Analyses of safety data

No formal inferential testing will be performed for either study period. Summaries will be descriptive in nature. All summaries of safety results described below will be presented for each study period respectively, unless otherwise noted.

General common rules

All safety analyses will be performed on the safety population for the double-blind period and on the OL population for the OL period, as defined in Section 2.3.2 unless otherwise specified, using the following common rules:

- Safety data in patients who do not belong to the safety population (ie, exposed but not randomized) will be listed separately.
- The baseline value for both double-blind and OL periods is defined as the last available value obtained up to the date and time of the first double-blind IMP injection in EFC14643 study, except otherwise specified.
- PCSA values are defined as abnormal values considered medically important by the Sponsor according to predefined criteria/thresholds based on literature review and defined by the Sponsor for clinical laboratory tests and vital signs, PCSA in children [Appendix A] and PCSA in adults version dated May 2014 [Appendix B]). Considering that the threshold defined in the PCSA list for monocytes and basophils can be below the ULN, the following PCSA criteria will be used for the PCSA analysis of monocytes and basophils:
 - PCSA criterion for monocytes: >0.7 Giga/L or > ULN (if ULN ≥ 0.7 Giga/L)
 - PCSA criterion for basophils: >0.1 Giga/L or > ULN (if ULN \ge 0.1 Giga/L)
- PCSA criteria will determine which patients had at least 1 PCSA during the TEAE period, taking into account all evaluations performed during the TEAE period, including nonscheduled or repeated evaluations.
- The treatment-emergent PCSA denominator by group for a given parameter will be based on the number of patients assessed for that given parameter at least once during the TEAE period.
- All measurements, scheduled or unscheduled, fasting or not fasting, will be assigned to analysis windows defined in Section 2.5.4, Table 5 and Table 6 in order to provide an assessment for Week 4 to Week 104 time points.
- In both the double-blind and the OL periods, for quantitative safety parameters based on central laboratory/reading measurements, descriptive statistics will be used to summarize results and change from baseline values by visit using analysis windows. Summaries will also include the last on-treatment value and the worst on-treatment value. The last on-treatment value is defined as the last value collected during the treatment period of each study period (see Section 2.1.4). The worst on-treatment value is defined as the nadir and /or the peak value during the treatment period of each study period according to the direction (minimum or maximum) of the abnormality as defined in the PCSA list.
- For exploratory purposes, key safety analyses for the double-blind period could also be provided according to up-titration/dose-adjustment status, ie, according to whether the patients remained on their initial dose or whether the dose was up-titrated/dose-adjusted. These analyses will be exploratory and descriptive (no formal comparison per dose) as it is expected that there could be inherent differences in the baseline characteristics between those patients up-titrating and those remaining on their initial dose. In order to reduce the

bias of this analysis, the period before the up-titration/dose-adjustment time point (planned at Week 12) will be analyzed separately since the early events occurring before Week 12 can only be attributed to the initial dose regimen (40 mg Q2W, 75 mg Q2W, 150 mg Q4W or 300 mg Q4W). Therefore the descriptive analysis per dose will include any safety events occurring from the first injection post Week 12 IVRS/IWRS transaction to the end of the TEAE period. Baseline characteristics of patients receiving each dose will be summarized.

2.4.5.1 Analyses of adverse events

Generalities

The primary focus of AE reporting will be on TEAEs. Pre-treatment and post-treatment AEs will be described separately.

If an AE date/time of onset (occurrence, worsening, or becoming serious) is incomplete, an imputation algorithm will be used to classify the AE as pre-treatment, treatment-emergent, or post-treatment. The algorithm for imputing date/time of onset will be conservative and will classify an AE as treatment emergent unless there is definitive information to determine it is pre-treatment or post-treatment. Details on classification of AEs with missing or partial onset dates are provided in Section 2.5.3.

Adverse event incidence tables will present the number (n) and percentage (%) of patients experiencing an AE by SOC, HLGT (when applicable), HLT (when applicable), and PT. Multiple occurrences of the same event in the same patient will be counted only once in the tables within a treatment phase. For tables presenting severity of events, the worst severity will be chosen for patients with multiple instances of the same event.

Sorting within tables ensures the same presentation for the set of all AEs within the observation period (pre-treatment, treatment-emergent, and post-treatment). For that purpose, the table of all TEAEs presented by SOC and PT sorted by the internationally agreed SOC order and decreasing frequency of PTs within SOCs (in the overall population) will define the presentation order for all other tables unless otherwise specified. The tables of AEs by SOC, HLGT, HLT and PT will be sorted by the SOC internationally agreed order and the other levels (HLGT, HLT, PT) will be presented in alphabetical order, unless otherwise specified.

Analysis of all treatment-emergent adverse events

The following TEAE summaries will be generated:

- Overview of TEAEs, summarizing number (%) of patients with any
 - TEAE.
 - Serious TEAE.
 - TEAE leading to death.
 - TEAE leading to permanent treatment discontinuation.

- Treatment-related TEAE.
- All TEAEs by primary SOC, HLGT, HLT, and PT.
- Number (%) of patients experiencing common TEAE(s) presented by primary SOC, HLT and PT (HLT incidence ≥5 % in any treatment group), sorted by SOC internationally agreed order and by alphabetic order for the other levels (HLT and PT);
- All TEAEs by primary SOC and PT, sorted by the internationally agreed SOC order and by decreasing incidence of PTs within each SOC (in the combined alirocumab group for the double-blind period and overall for the open-label period). This sorting order will be applied to all other tables by SOC and PT of TEAEs, unless otherwise specified.
- All TEAEs regardless of relationship in one column and, in the same table, a second column with TEAEs related to alirocumab according to investigator's opinion by primary SOC, HLGT, HLT and PT.
- All TEAEs by maximal intensity (ie, mild, moderate or severe), presented by primary SOC and PT, sorted by the sorting order defined above.

Analysis of all treatment emergent serious adverse event(s)

- All serious TEAEs by primary SOC, HLGT, HLT, and PT and by SOC/PT.
- All serious TEAEs by dose regardless of relationship in one column and, in the same table, a second column with TEAEs related to alirocumab according to investigator's opinion, by primary SOC, HLGT, HLT, and PT.

Analysis of all treatment-emergent adverse event(s) leading to treatment discontinuation

• All TEAEs leading to treatment discontinuation, by primary SOC, HLGT, HLT, and PT and by SOC/PT.

Analysis of groupings of adverse events including selected adverse events of special interest

All groupings of TEAEs including adverse events of special interest as listed in Section 2.1.4.1 will be analyzed using selections defined in Section 2.1.4.1 and will be presented by SMQ/CMQ and PT (when selection is based on SMQs/CMQs) and by SOC and PT (when selection is based on the e-CRF tick box or HLGT/HLT). The summaries will be sorted by decreasing incidence of PT within each SOC/SMQ (in the alirocumab group) for the double-blind period and overall for the open-label period.

In addition, the following variables will be tabulated for the local injection site reactions TEAEs:

- Intensity of the event (mild, moderate, severe).
- Number of events divided by the number of IMP injections.
- Time from first IMP injection to first injection site reaction.
- Description of the highest intensity of each symptom recorded in the specific e-CRF page.
- The use of the topical anesthetic will be assessed with regards to the occurrence of pain.

Besides, description of symptoms and possible etiologies for General Allergic Reaction TEAE reported by investigator (using the tick box), will be presented.

Analysis of pre-treatment and post-treatment adverse events

- All pre-treatment AEs by primary SOC and PT, sorted by the internationally agreed SOC order and decreasing incidence of PTs (in the alirocumab group) within each SOC;
- All pre-treatment AEs leading to treatment discontinuation by primary SOC and PT, sorted by the sorting order defined above;
- All post-treatment AEs by primary SOC and PT, sorted by the internationally agreed SOC order and decreasing incidence of PTs (in the alirocumab group) within each SOC;
- All post-treatment SAEs by primary SOC and PT, sorted by the sorting order defined above;

Analysis of treatment emergent adverse events related to COVID-19

The number of patients who experienced at least one TEAE related to COVID-19 will be described by primary SOC and PT (terms selected using the SMQ "COVID-19" narrow).

Analysis according to patients' status with regards to trial impact/disruption due to COVID-19

All TEAEs by primary SOC and PT will be presented according to trial impact/disruption due to COVID-19.

Subgroup of patients with two consecutive LDL-C <50 mg/dL or two consecutive LDL-C <25 mg/dL or two consecutive LDL-C <15 mg/dL

If applicable, summaries of TEAEs by SOC and PT and by SOC,HLGT,HLT and PT will be also provided on the safety subgroup population of patients with two consecutive results of LDL-C <50 mg/dL (and also those respectively <25 mg/dL, <15 mg/dL) (as defined in Section 2.1.5). Only TEAE for which it will be confirmed or unclear that they occurred, worsened or became serious the day or after the first level of LDL-C <50 mg/dL (respectively <25 mg/dL, <15 mg/dL) will be considered.

Analysis according to IVRS/IWRS BW strata

A summary of TEAEs, serious TEAE, TEAE leading to treatment discontinuation and local injection site reaction will be provided according to the baseline BW stratum (as per IVRS/IWRS) for the double-blind period.

Analysis according to previous participation to the Phase 2 DFI14223 study

A summary of TEAEs by SOC and PT and General allergic events will be provided on the safety population according to previous participation to the Phase 2 DFI14223 study.

Additional analysis for the OL period

The following summary tables will be added:

• The event rate per patient year (the number of patients with an event in question divided by total patient-years) will be provided for all TEAEs by SOC and PT. For a patient with event, patient year is censored at time of first event; for patient without event, it corresponds to length of the open-label TEAE period

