	 Proportion of patients achieving at least 30% reduction, 50% reduction in LDL-C at Week 24 (ITT and on-treatment estimands). 						
	 Proportion of patients achieving at least 30% reduction, 50% reduction in LDL-C at Week 12 (ITT and on-treatment estimands). 						
	 Percent change in LDL-C from baseline to Week 104 (ITT and on-treatment estimands). 						
	Other endpoints						
	 Serum alirocumab concentrations assessed throughout the study. 						
	Anti-alirocumab antibodies assessed throughout the study.						
ASSESSMENT SCHEDULE	Run-in period (as needed):						
	The run-in period is up to 4 weeks (+2 days), with 1 visit. Patients can enter the screening period as soon as the criteria for stable LMT are met and/or centralized genotyping data (if no clinical criteria or previous genotyping) is available.						
	Screening period:						
	The screening period is up to 2 weeks (+5 days) in duration. An intermediate/Day 1 visit for injection training may occur during which the patient, if aged \geq 12 (or another designated person such as parent, etc) will be trained to self-inject/inject with placebo. Patients can be randomized after injection training and as soon as eligibility is confirmed.						
	Double-blind treatment period:						
	The double-blind treatment period is 24 weeks in duration. Visits will be scheduled as follows: randomization visit (Day 1, Week 0), Week 8, Week 12 and Week 24 (end of the double-blind treatment period visit).						
	Open label treatment period:						
	The first open label treatment period visit will overlap with the end of double-blind treatment period visit. The second visit will take place at Week 32. Subsequent visits will be every 12 weeks until the end of the open label treatment period (ie, Week 44, Week 56, Week 68, Week 80, Week 92 and Week 104 [end of open label treatment period visit]).						
STATISTICAL CONSIDERATIONS	Sample size determination:						
	With a randomization ratio of 2:1 (alirocumab: placebo) for each dosing regimen cohort, a total sample size of 90 patients (30 in each alirocumab dosing regimen group and 15 in each placebo dosing regimen group) will have 92% power to detect a difference in mean percent change in LDL-C of 30% between each alirocumab dosing regimen group and its contemporaneously randomized placebo dosing regimen group. with a						

0.025 two-sided significance level per comparison and assuming a common standard deviation (SD) of 25%.

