6.4.2 Data Monitoring Committee

An independent DMC for pediatric studies will monitor patient safety by conducting reviews of accumulated safety data. The DMC will provide the Sponsor and the Steering Committee with appropriate recommendations on the conduct of the clinical trial to ensure the protection and safety of the patients enrolled in the study. In addition, the DMC will also institute any measures that may be required for ensuring the integrity of the study results during the study execution.

The DMC will be charged with reviewing the safety of patients with LDL-C <50 mg/dL (1.30 mmol/L) and more particularly, will review AE potentially associated with LDL-C <50 mg/dL (1.30 mmol/L) (see Section 10.6.2.3) in conjunction with the independent physician that is external to the EFC14643 study team and not part of any alirocumab activities. Only the independent physician will have access to the patient information during the double-blind treatment period. Details will be given in the DMC charter.

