2.1.5 Other endpoints

Other endpoints listed below are defined using same definitions and rules as for LDL-C, when applicable (see Section 2.1.3) and include:

- The absolute change in HbA_{1c} (%) from baseline to Week 24 in the double-blind period, as well as change from baseline to Week 68 and Week 104 in the OL period. PCSA criteria for HbA_{1c} will be also used (see Appendix A).
- The proportion of patients with 2 consecutives results, spaced out by at least 21 days, of LDL-C <50 mg/dL (<1.30 mmol/L), LDL-C <25 mg/dL (<0.65 mmol/L), LDL-C <15 mg/dL(0.39 mmol/L) during each treatment period (double-blind or open-label) and the time to the first LDL-C <50 mg/dL (<25 mg/dL, <15 mg/dL respectively) for these patients within the relevant treatment period.
- Cardiac function: CPK-MB and cardiac troponin (at Visit 4 [Week 0 / Day 1] and Visit 7 [Week 24]/or early termination) and in case of any clinically relevant cardiovascular effect observed in patients.
- The percent change in hs-CRP from baseline to Week 24 in the double-blind period. Hs-CRP values greater or equal to 10 mg/L will be excluded from analyses in a second approach, since these are suggestive of concurrent infections (1). PCSA (potentially

clinically significant abnormalities) criteria for hs-CRP will be also used (see Appendix A).

• Urine test at Visit 4 (Week 0 / Day 1) and Visit 7 (Week 24)/or early termination. Macroscopy will be performed at the central laboratory. If abnormal, then a standard microscope assessment will be conducted.

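### The adverse-event tables for patients with confirmed low LDL-C count events only from the first low value but report plain percentages, so read against the standard tables they can understate event frequency

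*SAP*

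**What the plan says.** - **Who is in the subgroup.** SAP 2.1.5 defines it through "The proportion of patients with 2 consecutives results, spaced out by at least 21 days, of LDL-C <50 mg/dL" (likewise <25 and <15 mg/dL), within the double-blind or the open-label treatment period.
- **Which events count.** SAP 2.4.5.1 includes a TEAE in these tables only if it is confirmed or unclear that "they occurred, worsened or became serious the day or after the first level of LDL-C <50 mg/dL", with the same rule at the two lower thresholds. Events of unclear timing are therefore kept. The tables are to be produced if applicable.
- **What is reported.** Under the general rules of the same section, "Adverse event incidence tables will present the number (n) and percentage (%) of patients experiencing an AE by SOC" and the lower MedDRA levels. No person-time measure, matched start date or comparator is specified for the low-LDL-C tables.
- **The standard window.** SAP 2.1.4 starts the double-blind TEAE period at the first dose. It ends 70 days after the last double-blind dose, or at the first open-label dose for patients who continue.
- **The one patient-year rate.** Under the additional open-label analyses in SAP 2.4.5.1, patients with an event are divided by total patient-years: "For a patient with event, patient year is censored at time of first event". It is planned for all open-label TEAEs, and its clock starts at the first open-label dose.

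**The concern.** Starting the count at the first low value is sensible, because an earlier event cannot be a consequence of low LDL-C. The difficulty is to combine that late start with a cumulative percentage. A percentage of patients with an event grows with the time over which events are counted. A reader will naturally set the low-LDL-C table beside the alirocumab and placebo TEAE tables, which count from the first dose. With the same underlying event rate, the low-LDL-C patients would then tend to show the lower figure.

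This table is meant to show whether low LDL-C carries extra harm. Protocol section 4 keeps cataract at very low LDL-C as a potential risk: 2.6% of alirocumab-treated adults with two consecutive values below 25 mg/dL, against 0.8% of those without. The protocol adds that this is a post-randomisation comparison and that there was no statistically significant difference from control groups. Protocol 6.4.2 also asks the DMC to review adverse events potentially associated with LDL-C below 50 mg/dL.

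**Working it through.** The documents give no coverage figure for these tables, so there is none to reproduce.

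**Inputs**
- Scheduled double-blind LDL-C: "at Week 8, Week 12 and Week 24 time points" (SAP 2.4.4.2.4; Protocol 1.3).
- Double-blind length: 24 weeks (Protocol, Clinical Trial Summary).
- TEAE window: Weeks 0 to 24 for a patient entering open label. For a completer who does not enter, last dose + 10 weeks; assuming the last dose is at Week 22, the window ends at Week 32.
- Membership needs a second low value at least 21 days later. On scheduled samples the first value of a pair is therefore at Week 8 or Week 12, because a first low value at Week 24 cannot be confirmed within the double-blind period.

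**Coverage** = (end of window − time of first low value) / length of window

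| | First low at Week 8 | First low at Week 12 |
|---|---|---|
| Enters open label | (24 − 8)/24 = 67% | (24 − 12)/24 = 50% |
| Completer, does not enter | (32 − 8)/32 = 75% | (32 − 12)/32 = 62.5% |

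For patients entering open label, the visit windows (±7 days at Weeks 8 and 12, ±3 days at Week 24) widen the range to about 45% (first low on Day 91, end on Day 165: 74/165) to 71% (Day 49, end on Day 171: 122/171).

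In open label, LDL-C is scheduled at Weeks 32, 44, 68 and 104. A first low value at Week 32, 44 or 68 leaves 72/80 = 90%, 60/80 = 75% or 36/80 = 45% of the 80 weeks.

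**Effect on a plain percentage.** Assume a constant hazard, the same before and after the first low value. If the full-window incidence is I and coverage is w, the table shows 1 − (1 − I)^w. For patients entering open label:

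| Assumed I | w = 2/3 (Week 8) | w = 1/2 (Week 12) |
|---|---|---|
| 5% | 3.4% | 2.5% |
| 30% | 1 − 0.70^(2/3) = 21% | 1 − 0.70^(1/2) = 16% |
| 60% | 46% | 37% |

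**What could be hidden.** The two percentages agree when hazard ratio × w = 1. A true hazard ratio after the first low value of 1/(2/3) = 1.5 (Week 8) or 1/(1/2) = 2.0 (Week 12) would therefore appear as no difference.

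The incidences in the table are illustrative. If events cluster early in treatment the gap is larger; if they come late it is smaller.

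**The case against.** A reader might infer that the plan contains no table with a comparable window. That is too strong. SAP 2.4.5 describes double-blind safety analyses by up-titration or dose-adjustment status that count events from the first injection after the Week 12 transaction, and it separates the earlier period to reduce bias. That is close to the window of a patient first low at Week 12. It is a partial match only: the analysis is optional, it is split by dose status and it does not fit a Week 8 start.

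A reader might also infer that the tables will understate harm. The documents do not establish this. The SAP names no comparator for the subgroup, and safety summaries are descriptive without formal testing. Keeping events of unclear timing pushes the count up, and the size of any shortfall depends on a hazard shape that no document gives. SAP 2.4.6 also plans Kaplan-Meier curves of time to first low LDL-C in the double-blind period, so the start of the window is itself reported.

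The practical weight is limited too. Protocol section 4 expects the chance of LDL-C below 50 mg/dL to be very low, and about 100 patients are planned on alirocumab. Individual review by the independent physician with the DMC is the main double-blind safeguard, and cataract is tabulated as a grouping of its own. Still, the subgroup need not be empty. Section 4 reports a mean reduction of 59.8% on 300 mg Q4W in Phase 2; from the 130 mg/dL entry threshold that is 130 × 0.402 = about 52 mg/dL.

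These points lower the priority. None of them supplies a person-time measure or a matched start for the low-LDL-C tables.

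**Conclusion.** The point holds as a gap in measurement and presentation. The low-LDL-C TEAE percentages cover about 67% or 50% of the standard double-blind window for patients continuing into open label, and about 75% or 63% for completers who do not. They carry no exposure measure that would make the difference visible. Compared with the standard tables they can understate event frequency at low LDL-C. These coverage figures rest on scheduled samples (SAP 2.5.5 also allows unscheduled ones) and, for the second pair, on a last dose at Week 22. The percentages in the working also need a constant hazard.

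One further feature works in the same direction. A patient who stops because of an event between the first and second low value never qualifies for the subgroup. A rate would not cure this, so it should be stated. The change is worth making because it is cheap, but nothing in the primary or key secondary analyses depends on it.

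**What to change.** In SAP 2.4.5.1, for each study period and threshold:

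1. Add patients with an event per patient-year from the first low value, censored at first event or at the end of the TEAE period, as in the existing open-label rate.
2. Beside it, show the same rate for placebo and for alirocumab person-time not yet at a low value. Count both from the first scheduled post-baseline LDL-C sample of the period: Week 8 in double-blind, and Week 32 in open label, where only alirocumab is available.
3. Split each alirocumab patient's time at the first low value. Do not define a never-low group: that would condition on the future, and a single Week 8 clock would not match patients first low at Week 12. Say where time after an unconfirmed low value goes.
4. Keep the percentages, with a footnote giving the shorter window and noting that membership requires a second low value at least 21 days later.

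The cost is SAP wording and one derived date per patient; the rate is already defined and trial conduct is unaffected. The downside is that rates from a small subgroup will be imprecise, and the comparison stays descriptive and post-randomisation.
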